## 8.6 Halting Rules

The stopping rules outlined below will be used to evaluate whether it is safe to proceed with dose escalation or whether the study should be suspended for further safety evaluation. If any halting criteria are met, enrollment and dosing for subjects will be suspended at all sites until the event is assessed by the SMC.

The SRC may be convened to provide an option for a rapid review of available safety data collected following the sentinel subjects in each group. Otherwise, confirmation by the site PI that the sentinel subjects did not meet any of the predefined objective criteria and approval by the DMID MM will suffice for expansion of enrollment in the rest of the subjects in each cohort. If any of the halting rules below are met, further dosing will be halted pending SMC review.

At predefined time points ([Section 8.7](#)), the SRC will meet to review all safety data for the cohort in question to determine if the escalation-halting rules have been met. In addition, the SDCC will provide study team with documentation of whether halting rules were/were not met after all the relevant safety data has been entered into the electronic data capture system up to Day 14 for subjects in the cohort. If none of the rules has been met through Day 14 into each cohort, the DMID MM will give approval for the next cohort to begin enrollment. If a

---

dose-escalation halting rule is met, the SMC will need to convene to recommend to DMID the next steps.

Dose-escalation decisions will be documented by the DMID MM. This documentation will include whether halting criteria were met and, if applicable, any review and actions of the SMC.

### **8.6.1      Sentinel Subject Halting Rules**

The site PI will review sentinel subject data from dosing through Day 4 to confirm that sentinel subject(s) data have not met predefined halting criteria and notify the DMID Medical Monitor prior to proceeding with dosing the remaining cohort.

- Any SAE, regardless of the relationship to the study product (with the exception of death or hospitalization that was the result of trauma or accident).

OR

- A sentinel subject within a cohort experiences a **related** Grade 3 or higher AE (laboratory or systemic) not resolved within 24 hours through Day 4. Resolution is defined as down to Grade 1 or Baseline. Note: If the event starts on Day 4, the review period will be extended to Day 5

If the predefined criteria for sentinel subject are met, the SMC will review the study data and provide guidance on how to proceed.

### **8.6.2      Cohort Dose-Escalation Halting Rules (Dosing through Day 14)**

- One subject has an SAE that is determined to be **related** to the study product.

OR

- Two or more subjects in a cohort experience Grade 2 or higher **related** AE (laboratory or systemic) that is coded in the same high level group term (HLGT) per MedDRA classification.

If the predefined criteria for dose escalation halting are met, the SMC will review the study data and provide guidance on how to proceed.

### **8.6.3 Study Halting Criteria**

- One subject has an SAE that is determined to be **related** to study product.
- OR
- Three or more subjects in the study (cumulative among all cohorts) experience a Grade 3 **related** AE (laboratory or systemic) that is coded in the same HLTG per MedDRA classification.

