#### **Severity of Event:**

Subjects who screened and enrolled prior to Protocol Version 11.0, AEs will be assessed by the investigator using a protocol-defined grading system (see Toxicity Table, [Appendix B](#)). For events not included in the protocol-defined grading system, the following guidelines will be used to determine severity:

- **Mild (Grade 1):** Events that are usually transient and may require only minimal or no treatment or therapeutic intervention and generally do not interfere with the subject's usual activities of daily living.
- **Moderate (Grade 2):** Events that are usually alleviated with additional specific therapeutic intervention. The event interferes with usual activities of daily living, causing discomfort but poses no significant or permanent risk of harm to the research participant.
- **Severe (Grade 3):** Events interrupt usual activities of daily living, or significantly affect clinical status, may require intensive therapeutic intervention, or death related to an AE. Severe events are usually incapacitating.

Subjects who screen and enroll with Protocol Version 11.0, AEs will be assessed by the investigator using the NCI CTCAE, Version 5.0 – November 2017. For events not included in the NCI CTCAE grading system, the following guidelines will be used to determine severity:

- Grade 1 (Mild): Asymptomatic or mild symptoms; clinical or diagnostic observations only; intervention not indicated.

---

- Grade 2 (Moderate): Minimal, local, or noninvasive intervention indicated; limits age-appropriate instrumental activities of daily living (eg, preparing meals, shopping for groceries or clothes, using the telephone, managing money).
- Grade 3 (Severe): Medically significant but not immediately life-threatening; hospitalization or prolongation of hospitalization indicated; disabling; limits self-care activities of daily living (eg, bathing, dressing and undressing, feeding self, using the toilet, taking medications, and not bedridden).
- Grade 4 (Life threatening): Urgent intervention indicated.
- Grade 5 (Death).

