### 8.1.2 Serious Adverse Events

An AE or suspected adverse reaction is considered an SAE if it occurs between the time of receiving study medication and the final study visit, and in the view of either the site PI or sponsor; it results in any of the following outcomes:

- Death,
- A life-threatening\* AE,
- Inpatient hospitalization or prolongation of existing hospitalization,
- A persistent or significant incapacity or substantial disruption of the ability to conduct normal life functions, or

---

- A congenital anomaly/birth defect.
- Important medical events that may not result in death, be life-threatening, or require hospitalizations may be considered serious when, based upon appropriate medical judgment, they may jeopardize the patient or subject and may require medical or surgical intervention to prevent one of the outcomes listed in this definition. Examples of such medical events include allergic bronchospasm requiring intensive treatment in an emergency room or at home, blood dyscrasias, or convulsions that do not result in inpatient hospitalization, or the development of drug dependency or drug abuse.

\*Life-threatening AE: An AE is considered “life-threatening” if, in the view of either the site PI or sponsor, its occurrence places the patient or subject at immediate risk of death. It does not include an AE that, had it occurred in a more severe form, might have caused death.

SAEs will be:

- Assessed for severity and relationship to study product and alternate etiology (if not related to study product) by a licensed study physician listed on the Form FDA 1572 or by the Institution as the site PI or sub-investigator.
- Recorded on the appropriate SAE data collection form and eCRF.
- Followed through resolution by a licensed study physician (for IND studies, a physician listed on the Form FDA 1572 as the site PI or sub-investigator).
- Reviewed and evaluated by DMID or SMC (periodic review unless related), and the IRB/IEC.

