## 14.3 Safety Data

### 14.3.1 Displays of Adverse Events

**Table 40: Overall Summary of Adverse Events – Participants in the Safety Population Enrolled Prior to Protocol v11.0**

	SAR440894 0.3 mg/kg (N = xx)		SAR440894 1 mg/kg (N = xx)		SAR440894 3 mg/kg (N = xx)		SAR440894 10 mg/kg (N = xx)		SAR440894 20 mg/kg (N = xx)		Placebo (N = xx)		All Participants (N = xx)	
Participants a with	n	%	n	%	n	%	n	%	n	%	n	%	n	%
At least one adverse event														
At least one related adverse event	x	x	x	x	x	x	x	x	x	x	x	x	x	x
Mild (Grade 1)	x	x	x	x	x	x	x	x	x	x	x	x	x	x
Moderate (Grade 2)														
Severe (Grade 3)	x	x	x	x	x	x	x	x	x	x	x	x	x	x
At least one severe (Grade 3) unsolicited adverse event														
Related	x	x	x	x	x	x	x	x	x	x	x	x	x	x
Unrelated	x	x	x	x	x	x	x	x	x	x	x	x	x	x
At least one serious adverse event	x	x	x	x	x	x	x	x	x	x	x	x	x	x
At least one related, serious adverse event	x	x	x	x	x	x	x	x	x	x	x	x	x	x
At least one adverse event leading to discontinuation of study product b														
At least one adverse event leading to early termination b														
At least one laboratory abnormality														
At least one related laboratory abnormality														
At least one clinically significant laboratory abnormality c														
Related														
Unrelated														
At least one not clinically significant laboratory abnormality c														
Related														
Unrelated														

Notes: N = Number of participants in the Safety Population

a Participants are counted once for each category regardless of the number of events.

b As reported on the Adverse Event eCRF.

c As reported on the Local Laboratory Results eCRFs.

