**Table 41: Overall Summary of Adverse Events – Participants in the Safety Population Enrolled Under Protocol v11.0**

	SAR440894 0.3 mg/kg (N = xx)		SAR440894 1 mg/kg (N = xx)		SAR440894 3 mg/kg (N = xx)		SAR440894 10 mg/kg (N = xx)		SAR440894 20 mg/kg (N = xx)		Placebo (N = xx)		All Participants (N = xx)	
Participants a with	n	%	n	%	n	%	n	%	n	%	n	%	n	%
At least one adverse event														
At least one related adverse event	x	x	x	x	x	x	x	x	x	x	x	x	x	x
Grade 1 (Mild)	x	x	x	x	x	x	x	x	x	x	x	x	x	x
Grade 2 (Moderate)														
Grade 3 (Severe)	x	x	x	x	x	x	x	x	x	x	x	x	x	x
Grade 4 (Life threatening)														
Grade 5 (Death)														
At least one Grade 3 (Severe) or Higher unsolicited adverse event														
Related	x	x	x	x	x	x	x	x	x	x	x	x	x	x
Unrelated	x	x	x	x	x	x	x	x	x	x	x	x	x	x
At least one serious adverse event	x	x	x	x	x	x	x	x	x	x	x	x	x	x
At least one related, serious adverse event	x	x	x	x	x	x	x	x	x	x	x	x	x	x
At least one adverse event leading to discontinuation of study product b														
At least one adverse event leading to early termination b														
At least one laboratory abnormality														
At least one related laboratory abnormality														
At least one clinically significant laboratory abnormality c														
Related														
Unrelated														
At least one not clinically significant laboratory abnormality c														
Related														
Unrelated														

Notes: N = Number of participants in the Safety Population

a Participants are counted once for each category regardless of the number of events.b As reported on the Adverse Event eCRF.c As reported on the Local Laboratory Results eCRFs.

**14.3.1.2 Unsolicited Adverse Events****Table 42: Summary of Adverse Events by MedDRA System Organ Class, High Level Group Term, Preferred Term, and Treatment Group – Participants in the Safety Population Enrolled Before Protocol v11.0**

[Implementation Note: If there is only 1 PT for an SOC and HLG, there will be no “Any PT” row.

Repeat for the following treatment groups: All Participants, SAR440894 0.3 mg/kg, SAR440894 1 mg/kg, SAR440894 3 mg/kg, SAR440894 10 mg/kg, SAR440894 20 mg/kg, Placebo]

Treatment Group	MedDRA System Organ Class	MedDRA High Level Group Term	MedDRA Preferred Term	n (%)	95% CI a	Number of Events
All Participants (N=X)	Any SOC	Any HLG	Any PT	x (x)	xx, xx	x

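### The study-wide halting rule in Protocol 8.6.3 counts Grade 3 related AEs only, so under the five-grade v11.0 scale a related Grade 4 AE not judged serious does not count

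*Protocol*

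**What the plan says.** Protocol Section 8.6 contains three predefined rules with an AE-grade threshold, each limited to related events.

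- **8.6.1, sentinel subjects:** a related "Grade 3 or higher AE (laboratory or systemic) not resolved within 24 hours through Day 4".
- **8.6.2, cohort escalation, dosing through Day 14:** "Two or more subjects in a cohort experience Grade 2 or higher" related AE in the same HLGT.
- **8.6.3, whole study:** "Three or more subjects in the study (cumulative among all cohorts) experience a Grade 3" related AE in the same HLGT. A single related SAE also halts the study.

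Section 8.1.1.1 (Severity of Event) uses two scales. For subjects enrolled before v11.0, Grade 3 is the top grade and its definition extends to events that "may require intensive therapeutic intervention, or death related to an AE". For subjects enrolled under v11.0 the scale is CTCAE v5.0, Grades 1 to 5; for events that CTCAE does not list, the fallback wording includes "Grade 4 (Life threatening): Urgent intervention indicated".

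The SAP adapted its AE displays to this change. The row "At least one severe (Grade 3) unsolicited adverse event" in Table 40 (before v11.0) becomes "At least one Grade 3 (Severe) or Higher unsolicited adverse event" in Table 41 (under v11.0).

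**The concern.** With *or higher* present in the two preceding rules, its absence from 8.6.3 cannot safely be read as shorthand, and neither document says that Grade 3 there includes Grade 4. The likely explanation is that the sentence was written for the three-grade scale, where Grade 3 was the maximum, and was not revised when v11.0 brought in five grades. Read literally, the rule is not monotone in severity: a worse event counts for less than a milder one.

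This matters because 8.6.3 is the only HLGT rule that accumulates across cohorts and the only one with no Day 14 limit. Escalation is decided on data through Day 14 while follow-up runs to Day 150, so earlier cohorts can still be in follow-up when later ones are dosed. A delayed or dispersed signal in this first-in-human escalation therefore depends on 8.6.3 for an automatic stop.

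A secondary, minor point concerns Section 8.5. It tells sites not to record isolated laboratory abnormalities as AEs and to put clinically significant ones on the laboratory form rather than a separate AE form. Section 8.1.1 treats clinically significant laboratory findings as AEs, and SAP Sections 6.7 and 15 also include related laboratory findings of any clinical significance. SAP Section 15 states its change for the final analysis and does not amend the site instruction.

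**Working it through.** The plan gives no operating characteristic for the halting rules, so there is no figure to reproduce. The check compares the rules with the grading scales and then applies the rule as written.

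**1. The rules side by side**

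| Rule | Related-AE grade | Subjects needed | Scope | Window |
|---|---|---|---|---|
| 8.6.1 | 3 or higher, unresolved within 24 h | 1 | sentinels | through Day 4 |
| 8.6.2 | 2 or higher, same HLGT | 2 | one cohort | through Day 14 |
| 8.6.3 | 3, same HLGT | 3 | all cohorts | no day limit |

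**2. Grades at or above 3, and what 8.6.3 does with them**

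- Before v11.0 the only such grade is 3. It is counted, so nothing is omitted.
- Under v11.0 the grades are 3, 4 and 5. The AE criterion counts Grade 3. A related Grade 5 is always an SAE and halts through the SAE criterion. A related Grade 4 halts that way only if it is judged serious.
- Grade and seriousness are separate judgements. Under Section 8.1.2 an AE is life-threatening only if, in the view of the site PI or sponsor, "its occurrence places the patient or subject at immediate risk of death".
- The grade left uncovered is therefore non-serious related Grade 4.

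**3. Effect on the count**

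Let *n* be the number of affected subjects in one HLGT and *k* the number whose only such event is a related non-serious Grade 4. As written, the halt requires *n* − *k* ≥ 3, so *n* = 3 + *k*: 3, 4 and 5 subjects for *k* = 0, 1 and 2. With *or higher*, *n* = 3 whatever *k* is.

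| Grades in three subjects | Count as written | Halt? | Count with *or higher* | Halt? |
|---|---|---|---|---|
| 3, 3, 3 | 3 | yes | 3 | yes |
| 3, 3, 4 | 2 | no | 3 | yes |
| 3, 4, 4 | 1 | no | 3 | yes |
| 4, 4, 4 | 0 | no | 3 | yes |

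With one event per cohort, 8.6.2 sees one subject against the two it needs. In the 3, 3, 4 pattern only the Grade 4 subject must be graded under v11.0; the other two may be on either scale.

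**4. Subjects in cohorts still to be dosed**

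Each cohort has 8 subjects, 6 of them active (Protocol Table 3-1). If the third event is in cohort *c*, later cohorts hold 8 × (5 − *c*) subjects, of whom 6 × (5 − *c*) are active:

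- *c* = 3: 16 subjects, 12 active (10 and 20 mg/kg)
- *c* = 4: 8 subjects, 6 active (20 mg/kg)
- *c* = 5: none

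The documents do not say in which cohort v11.0 took effect, so the range is all that can be given.

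**5. Follow-up outside 8.6.2**

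Scheduled post-dose laboratory days are 2, 3, 4, 7, 14, 28, 56, 84, 112 and 150 (Protocol Appendix A). Five of the ten (28 onwards) fall after Day 14. This shows when 8.6.2 is inactive, not how often the gap would occur.

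**The case against.** The strongest reply is that the uncovered class may be close to empty. An event that needs urgent intervention fits the important-medical-event criterion in Section 8.1.2, either the site PI or the sponsor may call it serious, and one related SAE halts the study. The CTCAE tables are not in the documents, so they do not establish how often a laboratory value would reach Grade 4 without clinical danger. The SAP's life-threatening category for laboratory results (Section 9.6) is a generic display; it also lists results that end in death. This narrows the gap but does not close it, because the important-medical-event criterion is itself a matter of judgement.

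Second, review continues even if no rule fires. The Medical Monitor must approve each new cohort or recommend convening the Safety Monitoring Committee (SMC) (Section 3.1), the Safety Review Committee sees each cohort's data through Day 14, and Section 8.6.4 allows suspension for a pattern of laboratory events. That stands: a signal need not be lost. These provisions are discretionary, however, whereas under Section 8.6 a met criterion suspends dosing at all sites until the SMC has assessed the event. What is lost is the automatic trigger, and with it mandatory independent review; apart from its organizational meeting and final data review, the SMC meets only ad hoc (Section 8.7.3).

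Third, the worked pattern is constructed. That is fair, and no frequency is claimed.

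On Section 8.5, the first instruction is partly a rule against recording a laboratory value and its diagnosis twice, and relationship, significance and grade are captured on the laboratory screen. All three halting rules expressly include laboratory events. The documents do not show that any would be missed.

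**Conclusion.** Section 8.6.3 is wrong as written and should be fixed. Its threshold omits a more severe grade that its companion rules include and that the SAP's v11.0 table includes. The gap is confined to related Grade 4 AEs in v11.0 subjects that are not judged serious and that fall across cohorts or start after Day 14. Each subject whose only event in the HLGT is of that kind raises the number needed to halt by one.

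The counts assume one event per subject in the HLGT, recorded at its highest grade, the Grade 4 event not judged serious, and no unresolved sentinel case under 8.6.1. The manual of procedures and the data coordinating center's halting program are not available. If that program already counts Grade 3 and above, the correction brings the protocol into line with it.

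The Section 8.5 inconsistency is minor, and the conclusion does not depend on it.

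**What to change.** In Section 8.6.3, change the threshold to *Grade 3 or higher* and confirm that the data coordinating center's halting check uses the same threshold.

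As a minor clarification, add one sentence to Section 8.5 stating that every related graded laboratory abnormality counts as an AE, is MedDRA-coded, and enters the 8.6.2 and 8.6.3 checks. This would align it with Section 8.1.1 and SAP Sections 6.7 and 15.

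The cost is two words and one sentence in a protocol amendment. The data needed are already on the laboratory screen, and no subjects, visits or samples are added.

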### **8.6.4 Infusion Halting Rules**

Infusion of the Investigational Product will be halted if any of the following manifestations of anaphylaxis develop and will not be restarted. Symptoms of anaphylaxis may begin in seconds or minutes of infusion.

- Skin or mucous membrane manifestations: hives, moderate or severe pruritus, or angioedema (usually of face, eyelids, or lips, tongue or uvula).
- Respiratory compromise: sensation of throat closure or choking, chest tightness, wheezing, stridor.
- A decrease in systolic BP to < 90 mmHg or > 30% decrease from baseline in systolic or diastolic BP.
- Tachycardia with an increase in resting heart rate to  $\geq$  130 beats per minute (bpm); or development of a ventricular dysrhythmia; or bradycardia < 45 bpm (or < 40 bpm in subjects with a baseline of < 60 bpm) that is associated with complaints of dizziness, nausea, or feeling faint.
- Syncope.
- Slurred speech and/or confusion.
- Any other condition that the site PI judges to unduly increase the risk to the subject.

---

Infusion related reactions to monoclonal antibodies typically develop within 30 minutes to two hours after the initiation of drug infusion, although symptoms may be delayed for up to 24 hours. The most common signs and symptoms of infusion reactions are:

- Fever and/or shaking chills
- Flushing and/or itching
- Alterations in heart rate and BP
- Shortness of breath, chest discomfort
- Nausea, vomiting, and/or diarrhea
- Various types of skin rashes.

In case of a suspected infusion-related reaction, the infusion can be stopped for up to 15 minutes and the subject observed to determine the severity of the reactions. For grading of infusion-related reactions, refer to [Appendix B](#) and NCI CTCAE, Version 5.0 – November 2017; see MOP for specific instructions regarding intervention. The decision to continue the infusion is based on the assessment by the investigator; depending on the assessment of the subject, supportive care can be administered, and/or the infusion permanently stopped.

The study may also be suspended (subject enrollment and/or study interventions suspended) because of safety findings, such as an SAE or an overall pattern of symptomatic, clinical, or laboratory events that the DMID Medical Monitor or the SMC consider associated with the study product. These may appear minor in terms of individual events, but might collectively represent potential concern for safety.

The DMID Medical Monitor may stop enrollment and/or administration of study product if AEs that meet the halting criteria are reported.

## **8.7 Safety Oversight (SRC, SMC)**

### **8.7.1 Data and Safety Monitoring Board**

Not applicable

### **8.7.2 Safety Review Committee**

The SRC will consist of a DMID Medical Monitor, Evotec medical officer, and the study/clinical site PIs. The SRC will review blinded combined safety data after each cohort.

Safety data may include, but is not limited to, vital signs, safety laboratory assessments, AEs, physical exam findings, and any noted trends through Day 14 for current cohort. The site PI(s) review the data in real time and share findings with the DMID MM and Evotec medical officer. The PI will indicate whether any cohort dose escalation halting rules or study halting criteria have been met and will provide a recommendation for dose escalation. Ad hoc SMC may be convened at recommendation of SRC in response to a safety issue.

### **8.7.3 Safety Monitoring Committee**

A SMC will be utilized for this study and will be comprised of individuals independent of the study, with relevant expertise, to advise DMID and the study investigators, will be established by DMID. SMC members will be separate and independent of study personnel participating in this study and should not have scientific, financial, or other conflicts of interest related to the study. The SMC will consist of members with appropriate expertise to contribute to the interpretation of the data from this study. The SMC will operate under the rules of a DMID-approved charter. DMID or the SMC chair may convene the SMC at specified times during the course of study as defined in the SMC Charter, or on an ad hoc basis according to protocol criteria, or if there are immediate concerns regarding observations during the course of the study. The SMC for this study will review data at the following time points:

- Organization meeting prior to the start of the study
- Ad hoc review: In response to a safety issue such as a study-halting or dose-escalation-halting rule being met.
- Final Data Review: An end of study summary of cumulative safety data will be provided for electronic review unless the SMC determines a data review teleconference is required.

After each meeting the SMC will make written recommendations to DMID whether the study (or intervention for an individual or study cohort) should continue per protocol, proceed with caution, be further investigated, be modified and then proceed, or be terminated.

---

